## 7 STUDY ACTIVITIES

### 7.1 Extension Study Enrollment Activities (Week 12 of Study APD334-003)

Eligible patients will have a detailed oral presentation of the nature, purpose, risks, and requirements of the extension study in addition to receiving detailed written information. They will have adequate opportunity to ask the appropriate person of the clinical staff (i.e., principal investigator or designee) presenting the study about any aspect of the study. Once the patient is satisfied that he/she is willing to participate in the study, he/she will be asked to sign the study VICF. The clinical personnel obtaining written consent from the patient will also sign the form to confirm consent has been obtained. Once signed, the investigator will retain the original for the patient's study records and provide the patient with a signed copy. The investigator will verify that informed consent has been obtained from each patient prior to admission into the study and prior to the patient undergoing any study-related procedures. If it is standard practice at the site to conduct a few general non-invasive study procedures (i.e., medical/social history, collection of concomitant medications, etc.) before a patient can be considered for a specific study, the study center must have a written SOP detailing the procedure, and also ensure that each patient signs a general consent prior to undergoing the general procedures.

The review of all inclusion and exclusion criteria will occur prior to a patient's transition from study APD334-003 into the extension study APD334-005, subsequent to obtaining informed consent.

#### 7.1.1 Treatment Assignment

Treatment assignment for APD334-005 will occur on Day 1 of APD334-005. All patients who complete the APD334-003 study and meet all the entry criteria and are eligible for the study will be assigned to 2 mg APD334 treatment. Select Week 12 results of APD334-003 study assessments will be carried over to study APD334-005 to serve as baseline assessments as outlined in Appendix 1.

### 7.2 Study Activities

#### 7.2.1 Baseline Activities – Day -1

[REDACTED] Selected Week 12 results of APD334-003 study assessments will be carried over to study APD334-005 to serve as baseline assessments as outlined in Appendix 1.

##### 7.2.1.1 Day -1 Activities

[REDACTED]

- 
- [REDACTED]
- Record adverse events
  - Record concomitant medications/procedures

## 7.2.2 Treatment Period

### 7.2.2.1 Day 1

Completers from the APD334-003 study who meet eligibility criteria for APD334-005 will have the following Day 1 procedures:

- Treatment assignment
- Diary review
- Vital signs
- [REDACTED]
- 12-lead ECG (per Appendix 1)
- Drug administration
- Drug dispensation
- Record adverse events
- Record concomitant medications/procedures

[REDACTED]

[REDACTED]

### 7.2.2.2 Week [REDACTED] Procedures

- PML checklist
- Urine pregnancy test (females only, not diagnosed as postmenopausal) [REDACTED]
- CBC with differential and platelets
- Clinical laboratory tests (serum chemistry, hematology, coagulation parameters, urinalysis and CRP) [REDACTED]
- [REDACTED]
- Diary review
- Vital signs

- 12-lead ECG (per Appendix 1)
- Drug administration
- Drug dispensation/accountability
- Record adverse events
- Record concomitant medications/procedures

#### 7.2.2.3 Weeks [REDACTED] Procedures

- PML checklist
- Pulmonary function test (spirometry) [REDACTED]
- Urine pregnancy test (females only, not diagnosed as postmenopausal) [REDACTED]
- CBC with differential and platelets [REDACTED]
- Clinical laboratory tests (serum chemistry, hematology, coagulation parameters, urinalysis and CRP) [REDACTED]
- Stool Sample [REDACTED]
- Fecal calprotectin [REDACTED]

- Diary review
- Vital signs

- 12-lead ECG (per Appendix 1) [REDACTED]
- Drug administration
- Drug dispensation/accountability
- Record adverse events
- Record concomitant medications/procedures

#### 7.2.2.4 Week 46/End-of-Treatment (EOT) or Early Termination Procedures

- Physical/ neurological exam
- PML checklist
- Urine pregnancy test (females only, not diagnosed as postmenopausal)
- CBC with differential and platelets
- Ophthalmoscopy with OCT (where available) and retinal photos
- Clinical laboratory tests (serum chemistry, hematology, coagulation parameters, urinalysis and CRP)
- Pulmonary function test (spirometry)
- Stool Sample

- Fecal calprotectin
- Flexible proctosigmoidoscopy
- [REDACTED]
- [REDACTED]
- Diary review
- [REDACTED]
- Vital signs
- [REDACTED]
- 12-lead ECG
- Drug administration
- Drug accountability
- Record adverse events
- Record concomitant medications/procedures

#### 7.2.2.5 2-week Follow-up Procedures, End of Study (EoS)

A 2-week follow-up visit to include additional safety assessments will be completed for all patients as outlined in the schedule of procedures and visits (Appendix 1). Patients will not receive study medication during the follow-up period.

---

## **8 DATA MANAGEMENT**

### **8.1 Data Collection**

All data (ECGs, clinical laboratory data, and all other study-related data) will be collected according to the sponsor or CRO's SOPs.

Upon database lock, which occurs after resolution of all queries, the CRO, if applicable, will provide statistical analysis software (SAS) transfer datasets to the sponsor and to the biostatistician for analysis using secure electronic data transfer per the sponsor's specifications.

### **8.2 Data Coding**

#### **8.2.1 Adverse Events**

Adverse events will be coded using the most current Medical Dictionary for Regulatory Activities (MedDRA) and tabulated, including categorical information of interest such as onset and resolution times, time of onset relative to dose, severity at onset, maximum severity, causal relationship to study medication, and action taken. Whenever possible, a constellation of signs and symptoms should be recorded as a unifying diagnosis (e.g., self-limited fever, runny nose, cough, and scratchy throat should be captured as an upper respiratory infection rather than by the individual signs and symptoms). AEs that occur after the first dose of study medication will be considered to be 'treatment-emergent'.

#### **8.2.2 Concomitant Medications and Non-drug Treatments**

Due to the variability in how medications are recorded, a standard naming convention is required in order to tabulate this data effectively. A common method of standardization is to categorize medications by their Preferred Term. In order to do this, medications will be coded using the World Health Organization Drug Dictionary (WHODRUG).

#### **8.2.3 Medical History**

Medical history will be coded using the most current MedDRA (version 18.0 or later).

---

## 9 PLANNED STATISTICAL METHODS

The statistical analysis of the data obtained from this study will be the responsibility of the CRO. Details of the statistical analyses will be included in a separate statistical analysis plan (SAP) which will be finalized prior to database lock. If after database lock changes are made to the pre-specified statistical analysis plan, the changes will be listed along with an explanation as to why they occurred in the Clinical Study Report.

### 9.1 Hypotheses and Objectives

#### 9.1.1 Objectives

##### 9.1.1.1 Primary Objective

[figure not shown]
The primary objective of this extension study is to evaluate the long-term safety and tolerability of APD334 in patients with ulcerative colitis who have completed the APD334-003 study.

##### 9.1.1.2 Secondary Objective(s)

The secondary objectives of the study are to evaluate the effect of APD334 on achieving and maintaining clinical response and/or remission in patients with ulcerative colitis after 46 weeks of treatment.

##### 9.1.1.3 Exploratory Objectives

The exploratory objectives of the study are to examine the effect of APD334 treatment in patients with ulcerative colitis on:

### 9.1.2 Hypotheses

There are no formal hypothesis tests specified in this study due to the lack of control treatment group.

## 9.2 Sample Size and Power Calculations

Patient enrollment is limited by the number of patients who complete the APD334-003 study. Therefore sample size and power calculation is not needed.

## 9.3 Analysis Populations

The analyses of all proportion based efficacy variables will use the Intent-to-Treat (ITT) population as primary. For other continuous efficacy endpoints, the Modified Intent-to-Treat (MITT) population will be used as primary. A completer's population will be used as a secondary analysis population for the efficacy endpoints.

### **INTENT-TO-TREAT POPULATION (ITT):**

This population consists of all enrolled patients, who received at least 1 dose of APD334 in the extension study.

### **MODIFIED INTENT-TO-TREAT POPULATION (MITT):**

This population consists of all enrolled patients, who received at least 1 dose of APD334, have a baseline measurement, and have a post-enrollment measurement in the extension study for the specific efficacy endpoint being assessed. Note that MITT population can vary with endpoints since some patients may have the needed data for inclusion in the MITT population for some endpoints but not for others.

### **COMPLETERS POPULATION (CP):**

This population consists of all patients who completed the extension study. No missing data will be imputed for this analysis. Any substantial differences between conclusions based on the ITT/MITT population and the completers' population will be investigated.

### **SAFETY POPULATION (SP):**

The Safety Population will include all enrolled patients who received study medication in the extension study.

## 9.4 Demographics and Baseline Characteristics

All baseline patient characteristics of demographic data (age, height, weight, race), ulcerative colitis history, social history (smoking status, caffeine intake, alcohol intake), medical history (abnormalities only), physical examination (abnormalities only), and concomitant medications at study entry will be listed for all patients.

Demographic data will be summarized and tabulated for the overall population. Continuous variables will be summarized using number of observations (n), mean, standard deviation (SD), median, minimum, and maximum. Frequencies and percentages will be reported for all categorical data

[figure not shown]
## 9.5 Efficacy Endpoints

### 9.5.1 Efficacy Endpoints

Secondary outcome measures are achievement, durability and maintenance of clinical response and/or clinical improvement. They include the following:

- The proportion of patients who achieve or maintain clinical response [defined as a decrease in 3-component Mayo Clinic score of  $\geq 2$  points and at least 30% with either a decrease of rectal bleeding of  $\geq 1$  or rectal bleeding score of 0 or 1] at Week 46 compared to APD334-003 baseline
- The proportion of patients who achieve or maintain clinical remission [defined as individual subscores of the 3-component Mayo Clinic score as follows: an endoscopy score (using flexible proctosigmoidoscopy) of 0 or 1, a rectal bleeding score of 0, and a stool frequency score of 0 or 1 with a decrease of  $\geq 1$  point at Week 46 compared to APD334-003 baseline

### 9.5.2 Exploratory Efficacy Endpoints

[figure not shown]
## 9.6 Statistical Methods

There is no between group inferential comparison for study endpoints. Summary statistical analyses will be performed for all efficacy measures. For proportion based measures, N, frequencies, proportion and its 95% confidence interval (CI) will be produced. For continuous measure, N, mean, median, range, and SD will be produced for observed values, and additional 95% CI for change or percent change from baseline will be produced if applicable.

### 9.6.1 Data Analysis for Secondary Efficacy Endpoints

The secondary efficacy outcome of achievement or maintenance of clinical response will be based on the proportion of patients who achieve or maintain clinical response [defined as a decrease in 3-component Mayo Clinic score of  $\geq 2$  points and at least 30% with either a decrease of rectal bleeding of  $\geq 1$  or rectal bleeding score of 0 or 1] at Week 46 compared to APD334-003 baseline using the ITT population. All patients who prematurely discontinue for any reason will be considered failures (non-responders) for all the proportion based endpoints. Similar analyses will be performed in terms of the other Week 46 proportion based endpoints such as proportion of patients achieving clinical remission and proportion of patients with endoscopic improvement.

For each study visit during the study, stool frequency and rectal bleeding subscores will be derived

- [Redacted bullet point]
- [Redacted bullet point]
- [Redacted bullet point]

All patients who prematurely discontinue for any reason will be considered failures (non-responders) for all the proportion based endpoints.

Descriptive statistics of N, mean or mean change, and standard deviation will be produced for continuous efficacy endpoints.

### 9.6.2 Data Analysis for Exploratory Efficacy Endpoints

[Redacted]

[Redacted]

[Redacted]

[Redacted]

- [Redacted]
- [Redacted]
- [Redacted]
- [Redacted]
- [Redacted]
- [Redacted]
- [Redacted]
- [Redacted]
- [Redacted]
- [Redacted]

[REDACTED]

- [REDACTED]

- [REDACTED]

#### 9.6.4 Multiplicity

Not applicable.

#### 9.6.5 Interim Analysis

No interim analyses are planned for this study.

#### 9.6.6 Data Safety Monitoring Board

Not applicable.

[REDACTED]

### 9.8 Safety Analysis

Safety and tolerability will be assessed by a review of all safety parameters including adverse experiences (AEs), laboratory safety parameters, vital signs, and ECG. Only summary tabulations (N, mean [or median], SD, mean [or median] change/percent change) and 95% CIs will be obtained. Adverse experiences will only be presented as summary tabulations. The analyses for all safety outcomes (categorical or continuous measures) will use the safety population which consists of all enrolled patients who received at least 1 dose of study drug in the extension study.

For analysis based on laboratory measurements, at least 1 laboratory test post-enrollment measurement in the extension study is required for inclusion in the safety population. When assessing change from baseline, a baseline measurement is also required. Baseline for the safety analysis is defined as the last pre-enrollment measurement. No missing data will be imputed for the safety analysis.

### 9.8.1 Adverse Events

Adverse events will be coded using the most current Medical Dictionary for Regulatory Activities (MedDRA) and tabulated, including categorical information of interest such as onset and resolution times, time of onset relative to dose, severity at onset, maximum severity, causal relationship to study medication, and action taken. AEs will be regarded as ‘pre-treatment’ if they occur between Screening and the time of administration of the first dose of APD334. All other AEs that occur after the first dose of study medication will be considered to be ‘treatment-emergent’.

Treatment-emergent AEs (TEAE) will be listed by patients. They will be summarized and expressed in terms of maximum severity and relationship to study medication. The incidence of TEAEs classified according to system organ class will be summarized. TEAEs will also be summarized by maximum intensity (assessed according to the Common Terminology Criteria for Adverse Events v4.0313 definitions) and relatedness to study medication.

Summaries of the number (%) of patients with at least 1 TEAE, classified according to MedDRA system organ class and preferred term, will also be provided for:

- Drug-related TEAE
- Treatment-emergent AEs leading to permanent discontinuation of study medication (study medication discontinued or withdrawal from study).
- Serious adverse events (SAEs)

Serious adverse events will be listed by patient. If there are no SAEs at the end of the study, the tables or listings will state that there are no SAEs in the study.

### 9.8.2 Physical Examinations

Physical examination results (abnormalities only) at each study visit will be listed.

### 9.8.3 Concomitant Medication

Pre-treatment and concomitant medication administered during the study will be listed. Concomitant medications will be coded using the WHODRUG Dictionary.

### 9.8.4 Vital Signs

Individual vital sign measurements will be listed and summarized using descriptive statistics. Summary statistics will also be provided for change from baseline in vital sign measurements. Baseline is defined as the last pre-enrollment measurement.

### 9.8.5 Clinical Laboratory Values

Individual lab values will be listed by visit, and summarized using descriptive statistics. Summary statistics will also be provided for change from baseline in lab values. Baseline is

---

defined as the last pre-enrollment measurement. Shift tables from baseline to last double-blind visit will also be produced for the laboratory assessments based on the categories of Low, Normal, and High. A clinically significant change from baseline may be recorded as an AE if deemed appropriate by the PI or sponsor.

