### 5.5.2 Blinding

The extension study is an open-label study.

In order to keep the blind of the induction study intact, the sponsor, patients, and personnel involved with the conduct of the APD334-005 study will continue to be blinded to the total WBC and lymphocyte counts, as access to this information may lead to unintentional unblinding of a patient (due to Investigational Product's mechanism of action). A central CRO physician(s) unblinded to the leucocyte count will continue to review and monitor the total WBC and lymphocyte counts for safety purposes in the trial. The study site personnel will not receive laboratory results for the total WBC or lymphocyte counts.

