## 6.8 Clinical Laboratory Tests

All details regarding clinical laboratory sample collection, preparation, and shipment are included in the laboratory manual provided by the local or central laboratory [REDACTED].

In the event of abnormal clinical laboratory values, the physician will make a judgment whether or not the abnormality is clinically significant and is deemed an adverse event.

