### 6.11.1 Adverse Event Reporting

Patients will be instructed that they may report AEs at any time. All events reported following study medication administration will be recorded as treatment emergent AEs (TEAEs).

Monitoring of ongoing AEs will be continued up to 30 days after study medication administration. In the event that an AE is not resolved or stabilized by this time, the sponsor in consultation with the investigator will decide whether to continue to monitor the AE or close-out the event in the database if no further follow-up is necessary.

For this study, an AE is defined as: “Any untoward medical occurrence in a study patient administered any dose of the study medication APD334 and which does not necessarily have to have a causal relationship with this treatment.” An AE can therefore be any unfavorable and unintended sign (including an abnormal laboratory finding), symptom, or disease temporally associated with the use of the study medication, whether or not related to the product. AEs can be any of the following:

- Unfavorable changes in general condition
- Subjective or objective signs/symptoms
- Concomitant disease or accidents
- Clinically relevant adverse changes in laboratory parameters observed in a patient in the course of a clinical study
- Pre-existing conditions which worsen in severity or frequency or which have new signs/symptoms associated with them

Adverse events will be elicited at the time indicated in the schedule by asking the question: “Since you were last asked, have you felt unwell or different from usual in any way?” Any adverse or unexpected events, signs and symptoms, will be fully recorded on the Adverse Event Form including details of intensity, onset, duration, outcome and relationship to the drug as determined by the PI. Whenever possible, a constellation of signs and symptoms should be recorded as a unifying diagnosis (e.g., self-limited fever, runny nose, cough, and scratchy throat should be captured as an upper respiratory infection rather than by the individual signs and symptoms). AEs may also be reported at any time. The type and duration of follow-up of patients after AEs will be documented.

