### 9.6. Lymphocyte Count

Summary tabulations (i.e. n, mean, SD, median, minimum and maximum) for the absolute lymphocyte counts, absolute changes from baselines [REDACTED], and percentage changes from baselines at each visit [REDACTED] will be presented for patients [REDACTED].

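### The plan does not say how low WBC or lymphocyte counts, hidden from investigators and sponsor, become adverse events, so the primary TEAE tables may under-count them

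*Protocol*

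**What the plan says.** **Who turns a laboratory change into an AE.** Protocol 9.8.5: "A clinically significant change from baseline may be recorded as an AE if deemed appropriate by the PI or sponsor". Protocol 6.8 gives the decision to a physician it does not identify further: "the physician will make a judgment whether or not the abnormality is clinically significant and is deemed an adverse event". Protocol 6.11.1 defines an AE broadly enough to cover "any unfavorable and unintended sign (including an abnormal laboratory finding), symptom, or disease temporally associated with the use of the study medication", and has the PI determine relationship to the drug. SAP 9.1.3 likewise gives relationship to the investigator.

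**Who can see the counts.** Protocol 5.5.2, repeated in SAP 4.3.2: "the sponsor, patients, and personnel involved with the conduct of the APD334-005 study will continue to be blinded to the total WBC" and lymphocyte counts. It adds: "The study site personnel will not receive laboratory results for the total WBC or lymphocyte counts". The exception is a central reviewer: "A central CRO physician(s) unblinded to the leucocyte count will continue to review and monitor the total WBC and lymphocyte counts" for safety. Protocol 6.8.1 refers back to that arrangement and adds no recording step.

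**What is tabulated.** The primary endpoint is TEAEs and serious TEAEs (SAP 3.2.1). SAP 9.1 tabulates them by relationship, by severity and for grade 3 or higher. Outside the AE tables, SAP 9.6 plans "Summary tabulations (i.e. n, mean, SD, median, minimum and maximum) for the absolute lymphocyte counts" together with changes from baseline. SAP 9.2 adds Low/Normal/High shift tables for relevant laboratory tests at the last scheduled post-baseline visit.

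**The concern.** The two parties named in Protocol 9.8.5 as judges of a laboratory AE, and the investigator who must attribute it, are the people from whom these two results are withheld. The one person who sees them has a monitoring task. The readable text gives that person no notification rule, no threshold, and no part in recording, grading or attributing an AE.

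This matters more here than for most analytes. Lymphocyte lowering is the drug's mechanism (Protocol 1, SAP 1), and 5.5.2 gives that mechanism as the reason for the blind. A low rate of leukopenia or lymphopenia in the primary safety tables could be read as long-term haematological safety when it may partly reflect who was allowed to see the result. No caveat to that effect is visible in the SAP.

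**Working it through.** No figure in the plan bears on this point, so the check is a cross-reading followed by a bound on the size.

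**Step 1. Follow one asymptomatic low count through the AE process.**

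| Step | Who acts | Source | Can that person see the count? |
|---|---|---|---|
| Review the result | Central CRO physician | Protocol 5.5.2, 6.8.1 | Yes |
| Judge clinical significance and AE status | An unspecified physician | Protocol 6.8 | Yes if the CRO physician is meant, no if the site physician is meant |
| Decide to record as an AE | PI or sponsor | Protocol 9.8.5 | No |
| Assess relationship | PI / investigator | Protocol 6.11.1, SAP 9.1.3 | No |
| Start the 24-hour SAE clock | Site personnel, on learning of the event | Protocol 6.11.2 | No |

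If 6.8 means the site physician, it conflicts with 5.5.2. If it means the CRO physician, it does not match 9.8.5. The sections need reconciling on either reading. The last row matters because 6.11.2 gives blood dyscrasias as an example of an important medical event.

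**Step 2. Bound the under-count.** Let k be the number of patients with an asymptomatic low count that would qualify as an AE, and p the share of these that the central physician passes on and that are then recorded.

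- Recorded = k × p
- Under-count = k × (1 − p)
- If p = 1, the under-count is 0. If p = 0, it is k.

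The documents give neither k nor p, so the range runs from none to all such events and cannot be narrowed.

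**Step 3. Ask whether the other count outputs fill the gap.**

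- *Shift tables (SAP 9.2).* Suppose a patient is Normal at baseline, severely low in mid-treatment and Normal again at the last scheduled visit. That patient appears as Normal to Normal. Among patients who end Low, a mild fall and a severe fall share one cell.
- *Baseline.* The APD334-005 baseline follows 12 weeks in APD334-003. A patient already lowered by active drug may start Low, and any further fall shows as Low to Low.
- *Summary statistics (SAP 9.6, and 9.2 for hematology).* A severe value enters that visit's mean and may set its minimum. The number of patients at that level is not reported.
- *Listings.* Individual values are listed (Protocol 9.8.5, 9.8.7; SAP 9.2), so the data for a per-patient count exist, but no visible output makes that count.

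**The case against.** The strongest reply has four parts.

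1. **The rule is not exclusive.** Protocol 9.8.5 is permissive, 6.8 leaves the physician unspecified, and the AE definition in 6.11.1 does not depend on who sees the result.
2. **Information can leave the blind.** Nothing readable forbids the central physician from notifying a site. Protocol 6.10.2 has patients return weekly until the lymphocyte count recovers, so someone who knows the count must prompt those visits. SAP 12 reports that blood-count follow-up tests for five patients went to local laboratories and that the sponsor was told.
3. **The counts are not lost.** They are listed, summarised and covered by the shift-table rule if treated as relevant tests. Clinical consequences such as infections remain reportable by sites.
4. **Text is redacted** in the relevant sections, and a separate safety plan may exist.

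A reader might infer that a laboratory change becomes an AE only through the PI or sponsor, so that low-count events are structurally absent from the TEAE tables and capture is essentially zero. Parts 1, 2 and 4 defeat that reading: a route that is not written down is not proof that none was used.

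The narrower point survives. The evidence in part 2 starts at the 2-week follow-up or after last treatment, so it shows no route during treatment. For the five patients, SAP 12 plans a narrative in the study report and mentions no AE records. The broad AE definition sharpens the problem, because these findings can be AEs that the named recorders cannot see. Part 3 limits the harm, but it does not supply a count of patients by severity.

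**Conclusion.** The concern holds as a gap between sections that can bias the primary safety tables in one direction. On the readable text, following the stated rules can leave asymptomatic leukopenia and lymphopenia under-counted in the TEAE, related-TEAE and grade 3 or higher tables. The visible count outputs do not correct for this, because none counts patients by their worst value.

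The under-count is not quantifiable, and any single percentage would be an assumption. A low reported rate should not be read as absence of these events, nor should the gap be read as proof that they were missed.

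The conclusion assumes that no redacted passage or separate safety plan sets out how the central physician's findings reach the AE database. Confidence is medium for that reason. It concerns total WBC and lymphocyte counts only, since the stated blind covers no other analyte.

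**What to change.** 1. **SAP 9.6 and 9.2.** Add the number and percentage of patients by worst on-treatment grade for lymphocyte count and for total WBC, shown against both the APD334-003 and the APD334-005 baselines. Use CTCAE v4.03, the scale already adopted in Protocol 6.11.3.
2. **TEAE tables.** Add a footnote that investigators and the sponsor were blinded to total WBC and lymphocyte counts, with a pointer to the new table.
3. **Protocol 5.5.2, 6.8, 6.11.1, 6.11.2 and 9.8.5, with SAP 9.1.3.** Reconcile who judges, grades, attributes and records AEs arising from these counts, and how the central physician's findings reach the AE database. The solution must keep the blind and also fit 24-hour SAE reporting and investigator-assessed relationship. Holding such events on a restricted form until database lock would not, by itself, meet the reporting clock.

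**Cost.** Items 1 and 2 need one table and one footnote from data already held, and they remain possible after enrolment has ended. Item 3 is a wording change plus a defined communication step. The downside is that the haematological profile may look less favourable, partly because an expected pharmacodynamic effect is now shown by grade. The accompanying text should say so.
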